8.6 Investigators responsibilities

Adverse events should be documented appropriately in the patient file. Such events may include changes in study drug treatment including possible interruption or discontinuation, starting or stopping concomitant treatments, changes in the frequency or nature of assessments, hospitalization, or any other medically required intervention. Once an adverse event is detected, it should be followed until its resolution, an assessment should be made at

each visit (or more frequently, if necessary) of any changes in its severity, its suspected relationship to the study drug(s), any of the interventions required to treat it, and its outcome. Information about common side effects already known about the investigational drug can be found in the 'Fachinformation' or will be communicated between updates in the form of Investigator Notifications. This information will be included in the patient informed consent and should be discussed with the patient during the study as needed.

8.7 Serious adverse events reporting

If an adverse event is serious (see definition in section 8.5), additional reporting to the sponsor is required:

The investigator must inform the sponsor of any SAE within 24 hours of being aware of the event. Information not available at the time of initial reporting should be provided in a follow-up.

Any SAEs experienced within 30 days after end of study treatment should only be reported to the sponsor if the investigator suspects a causal relationship to the study drug.

Information about all SAEs is collected and recorded on the Serious Adverse Event Report Form. All Serious Adverse Event Reports sent to the sponsor must include the patient number, age, sex, weight, height, severity of reaction (Grade 1-5 according to CTCAE criteria), relationship to study drug (related, probably related, possibly related, probably unrelated, unrelated, not assessed), date and time of administration of study medications and all concomitant medications, and medical treatment provided. The investigator must assess and record the relationship of each SAE to the study drug temsirolimus (certain, probable, possible, unlikely, unrelated), complete the SAE Report Form in English, and send the completed, signed form immediately by fax to the Safety Desk.

The original copy of the SAE Report Form and the fax confirmation sheet must be kept with the case report form documentation at the study site.

Follow-up information which becomes available as the SAE evolves, as well as supporting documentation (e.g. hospital discharge summaries) should be collected subsequently, if not available at the time of the initial report. Follow-up information is immediately sent to the

sponsor, using a new SAE Report Form stating that this is a follow-up to the previously reported SAE and giving the date of the original report.

Re-occurrence, complication, or progression of the original event should be reported as a follow-up to that event regardless of when it occurs. The follow-up information should describe whether the event has resolved or continues, if and how it was treated, and whether the patient continued or withdrew from study participation. An SAE occurring at a different time interval or otherwise considered completely unrelated to a previously reported one should be reported separately as a new event.

All Serious AEs whether related or unrelated to investigational product must be reported by confirmed facsimile transmission the complete SAE page to the address below. The fax confirmation should be placed together with the SAE form in the Investigator Site File.

Protocol-specific clarifications to this definition and exceptions for SAE reporting:

Myelosuppression, thrombocytopenia, anaemia and associated complications are expected events during leukemia therapy and are part of the treatment success (marrow emptying of leukemia cells). Therefore, myelosuppression-associated complications such as fever, infections, bleeding will be reported on the Adverse Events CRF as an adverse event even if it is associated with hospitalization or prolonged hospitalization.

In this context only prolonged myelosuppression, i.e. pancytopenia with marrow hypocellularity on day 42 or later from start of last cytotoxic therapy without evidence of leukemia, will require immediate reporting on an SAE form. This protocol-specific rule applies only for induction and consolidation courses, not during maintenance therapy.

In case a patient leaves this protocol to receive another more intensive cytostatic therapy (that is for persistent or recurrent disease), the following modification applies: AEs and SAEs occurring within 30 days after last protocol treatment and after first administration (day 1) of the other, more intensive therapy have only to be recorded on the present protocol when the investigator suspects the event to be related to this protocol treatment.

The investigator is responsible for assessment of seriousness, severity (CTCAE v 4.0) and causality of the SAE. The SAE form should be completed with as much information as possible. The investigator should not wait for full details before making the initial report.

If the event is fatal or life threatening, the investigator must fax any relevant follow-up information of the reported SAE to the Safety Desk within additional 8 days. In case of death, a copy of the autopsy protocol should be provided, if any. For SAEs, which are not fatal or life threatening, the investigator must fax follow-up information as soon as possible.

In case of death, the investigator has to supply sponsor, competent authority and Ethics Committee with all details requested.

Safety-Desk-Contact

Study Center of the Department of Medicine II Hematology / Oncology J.W. Goethe University Hospital [name] [name]

[contact]

For further information you may contact:

[contact]

It is the duty of the Safety Desk to inform the marketing authorization holder involved according to stipulation.

The initial SAE and follow-up SAE reports will be evaluated by the sponsor and if the SAE is not previously documented in the "Fachinformation" and is thought to be related to the study drug temsirolimus, the SAE Contact Center may urgently require further information from the investigator for Health Authority reporting. Suspected Unexpected Serious Adverse Reactions (SUSARs) will be collected and reported by the sponsor to the competent authorities and relevant ethics committees in accordance with Directive 2001/20/EC.

The Safety Desk will provide information for the Safety Data Monitoring Board as requested.

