4.2 Benefit / risk ratio

Patients eligible for this trial have a risk of treatment failure with standard chemotherapy of 70-80% at two years. Treatment failure is not compatible with long-term survival in these elderly patients. Included in these numbers are disease-related events (refractory disease, relapse) and treatment-related mortality that has to be expected to reach up to 10% in this patient group. The risk of this trial is that addition of temsirolimus to the standard treatment increases treatment-related mortality due to higher toxicity. Therefore the optimal temsirolimus dose level will be tested in the run-in part of this study, which will precede the randomized main part.

The possible benefit of the trial is to decrease the rate of treatment failure in the trial population. For a single patient, this could result in increased life-span, ideally without evidence of leukemia. Given the extensively high rate of treatment failure and the high toxicity of the currently available standard therapy, the medical need for novel, rational therapeutic approaches for this patient population is overwhelming. As pointed out above, the molecular rationale for the therapeutic administration of temsirolimus in AML is well founded. Thus, the Benefit/Risk ratio for a patient to participate in this trial seems very favorable.

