8.2 Severity of adverse events

Adverse events will be assessed according to the Common Toxicity Criteria for Adverse Events (CTCAE) version 4.0. If CTCAE grading does not exist for an adverse event, the severity of mild, moderate, severe, and life-threatening. CTCAE grade 5 (death) will not be used in this study; rather, this information will be collected in the End of Treatment or Survival Information CRF page. Adverse event monitoring should be continued for at least 30 days following the last dose of study treatment.

During the Run-in-Phase of the study, adverse events of all grades have to be documented in the Adverse Events CRF.

During the main part of the study, AEs grade 1 and grade 2 will be documented only in the patients file and AEs grade 3 and grade 4 will be documented in the Adverse Events CRF. (Since the majority of toxicities is expected from the underlying chemotherapy and is well known and documented in historic cohorts the documentation of adverse events will be restricted to grade 3-4.)

Symptoms of the disease under study should not be classified as AEs as long as they are within the normal day-to-day fluctuation or progression of the disease.

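### For induction and consolidation, section 8.7 leaves open whether fatal or life-threatening infections and bleeding in aplasia are reported as SAEs, and section 8.2 contradicts 8.4 and 8.7 on grade 5

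*Protocol*

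**What the plan says.** **The risk.** Section 4.2 states: "The risk of this trial is that addition of temsirolimus to the standard treatment increases treatment-related mortality due to higher toxicity". It expects "treatment-related mortality that has to be expected to reach up to 10% in this patient group".

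**The general rule.** Section 8.5 lists death and life threat as separate SAE criteria. Outside the hospitalization criterion, it excludes only events clearly due to progression of leukemia. Section 8.7 requires notice within 24 hours and adds: "All Serious AEs whether related or unrelated to investigational product must be reported by confirmed facsimile transmission".

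**The exception.** Under its protocol-specific clarifications and exceptions, 8.7 says: "myelosuppression-associated complications such as fever, infections, bleeding will be reported on the Adverse Events CRF as an adverse event", and that this holds even with hospitalization. The next sentence confines immediate reporting on an SAE form to a single event: "In this context only prolonged myelosuppression, i.e. pancytopenia with marrow hypocellularity on day 42 or later from start of last cytotoxic therapy". It applies when leukemia is not evident. The rule covers induction and consolidation courses and not maintenance.

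**Grading of death.** Section 8.2 says: "CTCAE grade 5 (death) will not be used in this study". It places death on the End of Treatment or Survival Information page and limits the main-part AE form to grades 3 and 4. Section 8.4 nevertheless lists fatal among the severity categories, and the SAE report in 8.7 must carry "severity of reaction (Grade 1-5 according to CTCAE criteria".

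**The concern.** The sentence that names prolonged myelosuppression as the only event needing an SAE form makes no exception for events that are fatal, life-threatening or suspected to be related to temsirolimus. It stands under a heading about exceptions, so a site may reasonably let it override the general rule. The events it touches are ones the drug may plausibly worsen. Section 6.2.4 names more severe and longer hematological toxicity as an overlap with chemotherapy, and 8.12.1.2 lists infection, pneumonia, sepsis and thrombocytopenia as temsirolimus reactions.

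At stake is how fast, and with what causality assessment, such an event reaches the Safety Desk, and whether all sites apply the same rule. The conflict over grade 5 adds a second inconsistency in how a fatal event is coded on the AE form.

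**Working it through.** The protocol gives no figure for this point that could be reproduced, so the check is mainly a comparison of text, with simple arithmetic for scale.

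**1. One case under two readings.** As an illustration, take a patient in first induction who dies of neutropenic sepsis on day 18.

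| Step | Literal reading of the exception | Narrow reading |
|---|---|---|
| What is waived | Every SAE criterion, except for prolonged myelosuppression at day 42 or later | Hospitalization or its prolongation only |
| Form | AE form | SAE form |
| Timing | AE assessment after each cycle (7.2) | Within 24 hours (8.7) |
| Relationship to temsirolimus | Related or unrelated (8.4) | Graded scale from certain to unrelated (8.5, 8.7) |
| Severity | At most grade 4 under 8.2, or fatal under 8.4 | Grade 1-5 (8.7) |

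- For the literal reading: the restricting sentence has no qualifier for death, life threat or suspected relation.
- For the narrow reading: the preceding sentence waives hospitalization by name: "will be reported on the Adverse Events CRF as an adverse event even if it is associated with hospitalization or prolonged hospitalization". Section 8.5 keeps death and life threat as criteria in their own right.

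**2. Do later clauses settle it?** Four were checked.

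- The additional 8-day follow-up for fatal or life-threatening events (8.7) concerns an SAE already reported, so it presupposes the report.
- Details of a death go to the sponsor, authority and Ethics Committee as requested (8.7). That sets no 24-hour duty.
- SUSAR screening (8.7) starts from initial and follow-up SAE reports.
- Sections 8.5 and 11.1 refer events judged possibly related to the DSMB. That category appears only on the scales given for SAEs, not in the two-way AE assessment of 8.4.

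None of these decides whether the day-18 death needs an SAE form. The first, third and fourth depend on that answer.

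**3. Grade 5.** Section 8.2 excludes grade 5, 8.4 includes a fatal category, and 8.7 asks for grades 1 to 5. Even without the exclusion, the main-part AE form would still stop at grade 4 under 8.2.

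**4. Scale.** The inputs are treatment-related mortality of up to 10% (4.2), 200 main-part patients at 100 per arm (9.1), and a safety interim at 50 evaluable patients per arm (11.1). Expected deaths = rate × n, assuming no temsirolimus effect.

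| Rate | Interim, per arm (50) | Full, per arm (100) | Total (200) |
|---|---|---|---|
| 10% (protocol's upper figure) | 0.10 × 50 = 5 | 0.10 × 100 = 10 | 0.10 × 200 = 20 |
| 5% (assumed, for comparison) | 0.05 × 50 = 2.5 | 0.05 × 100 = 5 | 0.05 × 200 = 10 |

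The share s of these deaths due to infection or bleeding in aplasia is not in the protocol. At the 10% ceiling, the number touched by the ambiguity is 20 × s: anything from 0 (s = 0) to 20 (s = 1). The text supports no narrower range.

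**The case against.** The strongest reply is that the exception, read in context, waives hospitalization and nothing else. It names only that criterion, and the restricting sentence refers back to it. Section 8.5 leaves death and life threat untouched, and 8.7 goes on to give follow-up times for fatal events and to ask for the autopsy protocol. This reading is fully open, and it is why the text cannot be called a settled exclusion. It does not remove the problem, because the restricting sentence also permits the literal reading and nothing later in 8.7 excludes it.

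A reader might infer something stronger: that treatment-related deaths drop out of safety oversight and that the DSMB cannot see them. The protocol does not support that.

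- Death is collected on the End of Treatment or Survival page (8.2) and counts in EFS and OS (9.5).
- Section 9.4 defines death in aplasia and death from indeterminate cause, so deaths can be classified to some extent.
- Grade 3 and 4 events stay on the AE form, with relationship to temsirolimus recorded (8.4).
- The DSMB confers regularly, has a safety interim, and may request any information if it has good reason to suspect excess risk. Its detailed tasks are left to a charter that is not shown (11.1).
- The exception does not apply in maintenance.

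All of this stands and limits the point to expedited, attributed reporting. It does not restore the 24-hour route. Under 8.7 the Safety Desk supplies the monitoring board as requested, and a death known only from a survival page brings no timely causality assessment.

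**Conclusion.** The point holds as a contradiction to be reconciled. For induction and consolidation, the restricting sentence in 8.7 conflicts with 8.5 and with 8.7's own rule that all SAEs are reported. On the literal reading, fatal and life-threatening infections and bleeding in aplasia lose 24-hour, attributed SAE reporting. On the narrow reading they keep it. Sites may therefore differ on the risk that 4.2 puts first. Separately, 8.2 contradicts 8.4 and 8.7 on grade 5.

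The size is bounded by the protocol's ceiling: up to about 20 treatment-related deaths in 200 patients, and about 5 per arm at the interim, if the 10% figure applies equally to both arms. With so few deaths, late or uneven reporting of even a handful would matter. No count of deaths actually affected can be given, because the share from infection or bleeding is not stated and because the count depends on how each site reads the text. The verdict does not rest on that count.

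**What to change.** **Section 8.7.** Limit the exception to the hospitalization criterion. Suggested wording: *Fever, infection or bleeding associated with expected myelosuppression during induction or consolidation need not be reported as an SAE when hospitalization or its prolongation is the only seriousness criterion met. Events that are fatal, life-threatening or suspected to be related to temsirolimus/placebo are reported as SAEs within 24 hours.* The existing requirement for prolonged myelosuppression can stay beside it.

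**Section 8.2.** Replace the grade 5 exclusion with a statement that fatal AEs are graded 5 with their cause. Extend main-part AE form documentation from grades 3-4 to grades 3-5 in both places where the limit is stated. Keep the instruction that death is also recorded on the End of Treatment or Survival page. Simply deleting the present sentence would lose that instruction and leave grade 5 events with no place on the main-part AE form.

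**Cost.** A short amendment that changes no treatment, plus some additional SAE forms for fatal, life-threatening or suspected-related events. The protocol gives no basis for estimating how many.

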8.8 Reporting of SUSARs

In case of the occurrence of a SUSAR it is the responsibility of the sponsor of the study to report these to the BfArM, the leading Ethics Committee, the Marketing Authorisation Holder as well as to the investigators of the trial – in line with the relevant national and European regulations. SUSARs will not be reported on national or international level to investigators of

other ongoing studies with the study drug and will not be reported to the IRBs of the participating centers.

The sponsor will inform relevant Regulatory Authorities and the Ethics Committee:

- of all relevant information about serious unexpected adverse events as
 defined above that are fatal or life threatening as soon as possible, and in
 any case no later than seven days after knowledge of such a case. Relevant
 follow-up information for these cases will subsequently be submitted within
 an additional eight days.
- of all other serious unexpected events suspected as defined above as soon as possible, but within a maximum of fifteen days of first knowledge by the investigator.

8.9 Annual Safety Reports

Once a year throughout the clinical trial or on demand, the sponsor shall provide the BfArM and the leading Ethics Committee with an annual safety report.

8.10 Birth control during study participation

Male patients whose sexual partners are women of child-bearing potential (WOCBP), must use an effective form of contraception (pearl index < 1%) during the study and at least 6 months thereafter. Effective forms of contraception are complete sexual abstinence, combined oral contraceptive, hormone IUCD, vaginal hormone ring, transdermal contraceptive patch, contraceptive implant or depot contraceptive injection in combination with a second method of contraception like a condom or a cervical cap / diaphragm with spermicide or surgical sterilization (vasectomy) in male patients. WOCBP are defined as sexually mature women who have not undergone a hysterectomy or surgical sterilization or who have not been naturally postmenopausal for at least 12 consecutive months (i.e., who has had menses any time in the preceding 12 consecutive months).

Prior to study enrolment, male patients who have WOCBP as partners must be advised of the importance of avoiding pregnancy during trial participation and the potential risk factors for an unintentional pregnancy. The patient must sign an informed consent form documenting this discussion.

Each pregnancy in a patient's partner must be reported to the sponsor within 24 hours of learning of its occurrence. The pregnancy should be followed up to determine outcome, including spontaneous or voluntary termination, details of the birth, and the presence or absence of any birth defects, congenital abnormalities, or maternal and/or newborn complications.

Pregnancy should be recorded and reported by the investigator to the Sponsor. Pregnancy follow-up should be recorded on the same form and should include an assessment of the possible relationship to the study drug of any pregnancy outcome. Pregnancy outcomes must be collected for the female partners of any males who took study drug in this study. Consent to report information regarding these pregnancy outcomes should be obtained from the mother.

8.11 Documentation of Concomitant Medication

During the induction and consolidation therapy a wide spectrum of concomitant medication is expected which is not relevant for the evaluation of the study drug. The documentation of concomitant medication will be restricted to:

- chemotherapy including steroids and intrathecal therapy
- irradiation
- antimicrobial prophylaxis (antibacterial, antifungal, antiviral)
- Growth factors
- Comedications known for CYP3A4 metabolism

Other concomitant medications such as standard supportive care including transfusions, antiemetic drugs etc. will not be documented routinely. In case of adverse events grade 3-4 the investigator will document possible correlation to concomitant medications.

Please refer to chapter 6.4 for concomitant and restricted therapies.

8.12 Warnings and Precautions

8.12.1 Investigational product (temsirolimus)

8.12.1.1 Summary of known adverse drug reactions

Hypersensitivity and known adverse drug reactions to the investigational product temsirolimus may include:

The most frequent adverse reactions (>30%) attributed to temsirolimus are rash, asthenia, mucositis, nausea, edema and anorexia. Due to frequency of gastrointestinal disorders antiemetic prophylaxis and therapy is required according to the study center's standard procedures.

Hematological toxicities are the second most common adverse reactions. Hematological grade IV toxicity is expected after induction and consolidation therapy. For the case that the time to hematological regeneration from the last chemotherapy course exceeds 42 days dose modifications of temsirolimus are required (see6.3.3).

Other frequent adverse reactions (>10%-30%) in patients receiving temsirolimus are bacterial and viral infections, dyspnoea, mucositis, diarrhea and pain.

As additional common adverse events are allergic/hypersensitivity reactions, an H₁ antihistamine should be administered in patients before starting the intravenous temsirolimus infusion.

Rare serious adverse reactions associated with temsirolimus include interstitial lung disease, bowel perforation and acute renal failure.

The most common laboratory abnormalities that occur with a frequency greater than 30% are hyperglycemia, hyperlipemia, hypertriglyceridemia, elevated serum alkaline phosphatase and elevated serum creatinine.

This may result in the need for an initiation or increase in the dose of hypergylcemic or lipid lowering therapy. Serum chemistry should be tested before and during treatment with temsirolimus regularly.

While there is no evidence that temsirolimus affects the ability to drive or operate machinery, patients experiencing vertigo or other symptoms that could interfere with their ability to drive a car or operate machinery should refrain from driving and operating machinery while under treatment with temsirolimus.

